2. Identify putative psychological mechanisms of response to CPT through pre-, mid-, and post-intervention measures of PTSD severity as well as measures of hopelessness, self-blame, and negative self-related thoughts.

Hypotheses:

NIMH Branch:

1. It is predicted that feasibility will be established by obtaining $\geq 80\%$ participant retention for the CPT course. As additional metrics of feasibility we will assess eligibility;

[†]For the NIMH branch, any historical data (i.e., information that is stable and is not expected to change over time) that has already been collected through protocol 2014-1106, we will obtain this data from the PI's database (2014-0350) and will not re-administer these assessments under the current protocol.

- participation; compliance; adherence; competence; and safety.
2. It is predicted that group CPT acceptability will be established by obtaining mean scores ≥ 27 on the CSQ-8.
 3. It is predicted that assessment collection feasibility will be established by obtaining 100% of PCL-5s at each timepoint for participants retained at that timepoint.

WPP Branch:

1. It is predicted that compared to the active control group, the CPT group will exhibit significantly greater reductions in PTSD symptom severity (primary outcome measure) as well as reductions in the severity of depression and general anxiety symptoms (secondary outcome measures) over the course of treatment.
2. It is predicted that the CPT group will exhibit greater reductions in hopelessness, self-blame, and negative self-related thoughts compared to the active control group.
 - a. Within only the CPT group, the reductions in hopelessness, self-blame, and negative self-related thoughts will precede the reduction in PTSD symptoms.
 - b. Within only the CPT group, the reduction in PTSD symptom severity will be mediated by reductions in hopelessness, self-blame, and negative self-related thoughts.

Trainee Project:

This study is part of the dissertation project of [name].

Participants:

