Therapeutic Alliance: Alliance will be measured using the Working Alliance Inventory-Short Revised (WAI-SR)^[31] and the California Psychotherapy Alliance Scale for Group Psychotherapy (CALPAS-P)^[32]. Participants will complete these at the one-week post-treatment timepoint.

Questionnaires:

All participants will complete the same battery of questionnaires and tasks at pre-, mid-, post-, one-month and three-month follow-up timepoints. This battery will include: PTSD Checklist for DSM-5 (PCL-5)^[33], Beck Depression Inventory-II (BDI-II)^[34], Beck Anxiety Inventory (BAI)^[35], Beck Hopelessness Scale^[36], the Posttraumatic Cognitions Inventory^[37], Buss-Perry Aggression Questionnaire (BPAQ)^[38], Impulsive Behavior Scale (UPPS-P)^[39], and Difficulties in Emotion Regulation Scale (DERS)^[40], Patient Health Questionnaire (PHQ-9)^[60].

The BDI-II will be reviewed by a study team member immediately after the participant completes it. If any participant indicates a desire to harm themselves or commit suicide, the research assistants will contact the prison medical staff. This is one of the only instances when the researcher would breach confidentiality (participant is risk to harm self, other, reveals plans to escape or start a riot). If participant expressed suicidal ideation during any assessments, we will follow up by using the Columbia-Suicide Severity Rating Scale Screen Version – Recent (C-SSRS-SV)^[41], a scale to rate the subject's risk. We will only ask about ideation within the last month (current). We will ask about suicidal ideation and intensity and any suicidal behavior. Participants will be considered at suicide risk if they endorse ≥ 2 on question #9 (suicidal ideation question) of the BDI-II or if they endorse any current plan to harm themselves. If a participant endorses a plan to hurt themselves, the C-SSRS-SV will be administered to determine suicide risk. If there are any imminent safety concerns (i.e., endorses current suicidal ideation/behaviors), research staff will notify the institution's psychologist, and the participant will be escorted by prison staff to the mental health services office.

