Analysis of effectiveness: Treatment efficacy will be determined by the change (from pre-intervention to post-intervention timepoints) for the primary outcome (PTSD) and secondary outcomes (e.g., depression) for each group. Repeated measures ANOVAs will be conducted for each group. One-way ANOVA will be used to test for group differences in score changes from pre-intervention to post-intervention, with follow-up pairwise tests (if warranted), using Tukey's post-hoc tests. IQ and age will be included as covariates in all analyses.

Exploratory analysis of moderators: As an exploratory follow-up analysis, we will examine potential moderators of effectiveness (details of measures in "Baseline Assessments" above). Following published guidelines for randomized controlled trials [45,46], moderators of treatment outcome will be tested in regression models, in which the post-intervention primary outcome measure (PCL-5 score) is regressed simultaneously onto 1) dummy-coded group assignment (CPT vs control), 2) the hypothesized moderator, 3) the group x hypothesized moderator interaction, 4) the pre-intervention primary outcome measure (PCL-5 score), and 5) any covariates of non-interest. The regression coefficients of interest are the main effect of the moderator and its interaction with group. A main effect independent of an interaction indicates the moderator predicts symptom reduction regardless of group assignment. An interaction with group indicates that the moderator predicts symptom reduction more strongly in one of the treatment conditions (i.e., specificity of moderation).

Adherence by the therapists will be measured by ratings of the presence or absence of five session elements (scores 0-5) by the clinical supervisors, as in previous CPT studies [16,18]. Adherence ratings will be collected for two audiotaped group sessions out of each 12-session intervention (16.7% of sessions). Our study goal is adherence scores ≥ 4 for each session.

Competence of the therapists will be measured by ratings of the quality of session elements (scores 1-7; 1="not satisfactory", 4="satisfactory", 7="excellent") by the clinical supervisors, as in previous CPT studies [16,18]. Competence ratings will be collected for two audiotaped group sessions out of each 12-session intervention (16.7% of sessions). Our study goal is competence scores ≥ 4 for each session.

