Specific Aim #2: To measure previously established mediators of CPT efficacy (hopelessness, self-blame, and negative self-related thoughts), as in previous studies with non-incarcerated populations [47-49], we will administer the Beck Hopelessness Scale [36] and the Posttraumatic Cognitions Inventory [37].

Statistical test of mediation: Mediation analyses will be conducted according to published guidelines for randomized controlled trials [45,46] in order to determine the extent to which changes in the proposed mediators of treatment effectiveness (described above) account for decreases in PTSD symptom severity (PCL-5 score) over the course of treatment. These mediation analyses will be conducted with regression models, in which the hypothesized mediator is regressed onto group assignment controlling for pre-intervention mediator measures (i.e., path a), and the post-intervention PCL-5 score is regressed onto the post-intervention mediator measure, controlling for pre-intervention measures and group assignment (i.e., path b). The indirect mediation effects (i.e., product of a and b paths) will be calculated using bootstrapped confidence intervals [49]. Statistical significance of the indirect effect will be concluded if the confidence interval of the indirect effect does not include zero.

Current Alternatives to Research Participation:

Participation in this study will have no effect on the availability of other treatments for potential participants. Participants may have the opportunity (or be required) to engage in other corrections-based treatment groups based on their criminal history (e.g., substance abuse treatment, domestic violence treatment, sex offender treatment, anger management), however there is no evidence that these treatment protocols influence PTSD symptomology. Outside of group therapy, incarcerated individuals may have the opportunity to meet individually with a licensed psychologist or psychiatrist semi-regularly (e.g., monthly) depending on their diagnosis and level-of-need.

Participant Recruitment:

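### WPP hypotheses 2a and 2b concern the CPT arm alone, but the one planned mediation model compares arms using same-visit scores, so it tests neither as worded

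*Combined protocol and SAP*

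**What the plan says.** Under Hypotheses, WPP Branch, parent hypothesis 2 compares the arms on reductions in the three mediators. The two sub-hypotheses then change population:

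- 2a: "Within only the CPT group, the reductions in hopelessness, self-blame, and negative self-related thoughts will precede the reduction in PTSD symptoms".
- 2b: "Within only the CPT group, the reduction in PTSD symptom severity will be mediated by reductions in hopelessness, self-blame, and negative self-related thoughts".

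WPP objective 2 (Overall Study Objectives) is to "Identify putative psychological mechanisms of response to CPT through pre-, mid-, and post-intervention measures of PTSD severity", together with the mediator measures.

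The analysis is in Measurement of Specific Aims, WPP Branch, Specific Aim #2, Statistical test of mediation:

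- Path a: "the hypothesized mediator is regressed onto group assignment controlling for pre-intervention mediator measures (i.e., path a".
- Path b: "the post-intervention PCL-5 score is regressed onto the post-intervention mediator measure", adjusting for pre-intervention measures and group assignment.
- The product of the paths gets a bootstrap interval and is declared significant if the interval excludes zero.

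The Questionnaires section says "All participants will complete the same battery of questionnaires and tasks at pre-, mid-, post-, one-month and three-month follow-up timepoints". That battery contains the PCL-5, the Beck Hopelessness Scale and the Posttraumatic Cognitions Inventory, so mid-treatment values of both mediator and outcome will exist.

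**The concern.** 2a is a claim about order, and the only model that links mediator to outcome contains none. 2b is a claim about one arm, and the model is built on the contrast between two. Followed exactly, the plan leaves 2a untested and answers 2b with the estimate of a different quantity.

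The practical risk is in the reporting. The plan's decision rule produces a significant or non-significant indirect effect, and no other analysis speaks to order. A significant result could then be written up as cognitions changing first. Symptom improvement that drives cognitions, or a cause shared by both, can produce the same result. The protocol itself describes candidates for a shared cause: therapy groups of 6-8 members (Treatment) and individual contact with a psychologist or psychiatrist outside the groups (Current Alternatives to Research Participation).

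**Working it through.** The plan gives no figure for this aim. Its one sample-size calculation (Statistical Considerations) is for NIMH retention, n = 32, and the WPP branch adopts that number. The check is therefore mainly textual, with a simulation to show direction.

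**1. Is order analysed anywhere?** The Aim 1 paragraph covers change "for the primary outcome (PTSD) and secondary outcomes (e.g., depression) for each group. Repeated measures ANOVAs will be conducted for each group"; the mediators are not named. The moderator regressions use baseline variables. The PCL-5 is completed at every session, but the mediators are listed only for the testing visits. Path a states no visit for the mediator, and neither path names a mid-treatment value. No lagged or change-timing analysis appears.

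**2. Can path a be fitted within CPT?** The model is M = a0 + a·G + a1·M0. With G = 1 for everyone, the group column equals the intercept: three columns, rank 2. So a, and hence a × b, is not estimable in the CPT arm.

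**3. What is path b?** P2 = b0 + b·M2 + b1·M0 + b2·P0 + b3·G. The group term removes the difference between arms, so b is a pooled within-arm slope. With no group × mediator term, it equals the CPT slope only if the slopes are equal across arms. In an assumed extreme case (mediator–PCL-5 slope 1.2 in control, 0 in CPT, 60 per arm), the planned test was significant in 99% of runs, while the CPT-only slope averaged about 0 and was significant in 4%.

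**4. Does a positive result imply order?** All parameters here are assumed.

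- Arm sizes: 32 and 60 (Statistical Considerations) and 40 (half the stated WPP total of 80).
- Standardised scores: P = PCL-5, M = mediator, visits 0/1/2 = pre/mid/post; baseline SD 1 and correlation 0.5; residual SD 0.7.
- Treatment effect d = 0.3 or 0.5; cross-effect c = 0.2, 0.35 or 0.5; SD of the common cause U = 0.3, 0.5 or 0.7.
- Two covariates with no effect stand for IQ and age.
- CPT-arm lag: 4000 trials per setting, two-sided 5%, reliability 1.0 and 0.85. Planned model: 400 trials, 400 bootstrap draws, 95% percentile interval, reliability 1.0 (reverse causation also at 0.85).

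The CPT-arm lag regresses P2 on M1, adjusting for P0, P1, M0 and the covariates.

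| Scenario | Generating model | Planned test significant | CPT-arm lag significant |
|---|---|---|---|
| Reverse causation, no M effect on P | Pt = 0.7·Pt−1 − dG + e; Mt = 0.6·Mt−1 + c·Pt + e | 4% to 87% | 4% to 7% |
| Common cause, no M effect on P | Pt = 0.7·Pt−1 − dG + U + e; Mt = 0.6·Mt−1 − dG + U + e | 28% to 98% | 8% to 72% |
| M acts in the same interval | Mt = 0.7·Mt−1 − dG + e; Pt = 0.6·Pt−1 + c·Mt + e | 32% to 100% | 10% to 51% |
| M acts at the next visit | M as above; Pt = 0.6·Pt−1 + c·Mt−1 − 0.2G + e | 7% to 72% | 12% to 94% |

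A second set of assumptions with stronger effects (treatment effect 0.8, slope 0.6) gave planned-test significance of 100% when the mediator moved first and 90% when PTSD moved first, at 60 per arm (96% and 62% at 32). Lag power there was 87% at 32 and 99% at 60. The percentages move with the assumptions. In both sets the planned test can be significant often when the order runs the wrong way.

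**5. Does the lag test all of 2a?** No. When the mediator fell first on average and PCL-5 fell later, with no person-level link between them, the lag rejected in 5% of trials at 32, 40 and 60. It tests whether earlier mediator levels predict later symptoms between persons, not the average timing of change.

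**The case against.** The strongest defence is that the two-arm model is a legitimate mediation analysis of the randomised effect, that its path a serves parent hypothesis 2, and that path b, being adjusted for group, already is a within-arm slope. All of this stands. A reader might infer that the mediation analysis is invalid or that efficacy is compromised; the documents support neither. The gap is between the model and the wording of 2a and 2b.

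The plan also cites published mediation guidelines (references 45 and 46). Their content cannot be checked here, and a citation does not specify a lagged or CPT-only model when the model written out has neither.

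The objection to a lagged model is fair too: it is open to a common cause, often weak at these sizes, and does not test average timing. A reader might expect it to prove order; it would not. That is why it should be exploratory, and why rewording 2a is an equal alternative.

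Two further inferences should be resisted. The upper figure of 87% is not an error rate for this trial, because every parameter is assumed. Nor can power be scaled down by the 60% and 80% rates in Statistical Considerations: those are NIMH rates of attending all sessions, not WPP loss of assessments.

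**Conclusion.** The concern holds on the text. The planned analysis does not test 2a, because it contains no order, and does not estimate 2b as worded, because a × b does not exist within the CPT arm. It does estimate mediation of the CPT-versus-control effect. The simulated ranges support one conclusion only: a significant planned indirect effect must not be read as cognitions changing first. They do not estimate how often that would happen here.

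This should be corrected before outcome data are analysed. Mechanism is one of the two stated WPP objectives, but the primary efficacy comparison is not affected.

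**What to change.** 1. **2a.** Add an exploratory CPT-arm model: post PCL-5 on mid mediator, adjusting for pre and mid PCL-5 and pre mediator. Report the reverse lag beside it (post mediator on mid PCL-5, adjusting for pre and mid mediator and pre PCL-5). Adjust over the three mediators, for example by Holm; unadjusted, three independent tests give 1 − 0.95³ = 14% false positives. State that the model tests between-person prediction and not average timing, is open to a common cause including shared therapy groups, and has low power at these sizes. At 0.05/3, simulated power was 4% to 35% (same interval) and 5% to 87% (next visit). Alternatively, reword 2a and say that order is not tested.
2. **Covariates.** The Aim 1 paragraph says "IQ and age will be included as covariates in all analyses". Apply this where the data exist in WPP. The IQ source is unclear: Baseline Assessments takes it from protocol 2014-1106, Measures and Assessments rules out that protocol's data for WPP, and Vulnerable Populations uses the Consent Quiz as the measure of intellectual ability.
3. **2b.** Either reword it as mediation of the CPT-versus-control effect, or specify a CPT-arm model of PCL-5 change on mediator change, reported as association only. Under reverse causation or a common cause, that model was significant in 20% to 100% of simulated trials.
4. **Planned model.** Keep it, name the visit of the path-a mediator, and state that it does not establish order.

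The cost is analysis wording; the mid-treatment scores are already collected.

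One matter should be raised as a separate point. In Research Design and Procedures, WPP Branch, mid testing falls between sessions 5 and 8, and post testing within a week after week 6. With weekly sessions these are about weeks 5 to 8 and weeks 6 to 7, so the windows can overlap and the statements must be reconciled. Any lagged model needs mid testing to precede post testing.

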Participants will be reconsented using the updated consent form from the CP021 change, which informs them about the collection of RHU placements, conduct reports, clinical observations, reconviction, and re-incarceration through public records and/or requests from the Department of Corrections database. We will try to schedule two meetings for participants still housed at TCI to minimize the burden on facility staff. Facility staff will send a movement slip for them to meet with the UW project, and if they don't show up, we will call them down using the phone with a CO present. The re-consent process will only occur in person, as video calls would place an additional burden on facility staff and require more resources.

In the single branch version of this protocol prior to CP006, we enrolled 70 participants since that enrollment our protocol was revised, since then this is now a two-branch study. Our target enrollment thus includes the prior 70 participants from the prior protocol.

For the current two branch protocol, up to a total of 172 incarcerated individuals (76 male and 76 female) will participate in group assignment. To account for potential participant attrition between consent and group assignment (e.g., due to transfer, release, segregation) we will enroll a total of up to 270 participants (taking into account single-component version enrolled participants) based on eligibility from participation in protocol 2014-1106. Over the course of the study, we will run twelve rounds of CPT sessions; these rounds will include 12 CPT sessions occurring twice a week for a total of 6 weeks. Six of these rounds will be conducted at TCI, and Six will be conducted across OCI and FLCI. In addition, WPP branch of the study involves a waitlist control group; this group will receive the CPT treatment after the treatment group completes the treatment. Participation in the waitlist control group will not affect participation in any other treatments that are available at the facilities. Sessions will be conducted at TCI and across OCI or FLCI.

Vulnerable Populations:

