Participants will be assigned to a CPT group if they meet PCL-5 criteria for a current probable PTSD diagnosis. CPT groups will engage in 12, 90-minute treatment sessions (18 hours total). With the optional opportunity to take 15-20 minutes after each session to de-stress and calm down if necessary. These sessions will take place over 6 to 12 weeks, depending on session frequency. The CPT group-members are also asked to complete weekly homework (approximately 12 hours total) as well as a post-intervention focus group and will have one follow up CPT session 6-8 weeks post-treatment. A maximum of 8 participants, but no less than 3 will be included in each CPT group. Participants will be able to continue any ongoing treatment/interventions they are engaged in within the institution as long as it meets our eligibility requirements.

In addition to the treatment groups, CPT group members will also complete a number of additional testing sessions throughout the course of treatment. They will participate in a pre-treatment testing session two weeks prior to the start of treatment. They will be asked to complete the PCL-5 at the beginning of each treatment session. After treatment session 5, group members will complete mid-treatment testing assessments. Participants will be called down individually to complete these assessments in a private room with a research assistant after completing the 5th therapy session,

[†] For the NIMH branch, any historical data (i.e., information that is stable and is not expected to change over time) that has already been collected through protocol 2014-1106, we will obtain this data from the PI's database (2014-0350) and will not re-administer these assessments under the current protocol.

but before completing the 8th therapy session. Group members will then complete post-treatment testing within one week after completing treatment (group session 12). One month after the treatment is completed, group members will complete the first round of follow-up testing. Three months after the treatment is completed, group members will complete the final round of follow-up testing. Post-one-month, and three-month follow up-testing will follow the same procedure as pre- and mid-testing. In total, group members will be asked to complete 18 sessions in total (pre-, mid-, post-, one-month follow up-testing, three-month follow-up testing, 12 treatment groups, and 1 post-intervention focus group).

WPP Branch:

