Research activities conducted at non-UW sites (OCI, FLCI, TCI) will be monitored by experienced research staff (graduate students, Research Specialists, P.I.) to ensure that the activities are within the guidelines of the protocol. Research team members will be trained to conduct the research activities according to IRB guidelines and will immediately report any complications to the research staff and the P.I. The P.I. will meet weekly with the entire study team to ensure regular communication regarding the study procedures. Any unanticipated problems, adverse events, or protocol deviations will be monitored by the study therapists and will then be reported to [name]. Examples of potential reportable events include participant drop out due to unexpectedly high emotional distress from participating in the group or a participant report of significant increase in suicidal ideation. [name] will relay these events to the UW-Madison HS-IRB. If any protocol changes are necessary in response to an unanticipated problem, [name] will communicate this to the UW-personnel working on the study, and the study therapists will monitor such changes on-site to ensure they are followed.

Because the multiple study sites are not involved in the research study (the studies are simply conducted at these sites), communication between research staff and the study sites is limited to logistics of scheduling (e.g., reserving rooms in the prison). Specific study information (e.g., protocol updates) will not be disseminated to the study sites.

The UW-Madison HS-IRB is the only IRB that will be approving documents and consent forms for this study. Therefore, there is no need to review IRB approved documents from other sites.

Monitoring and Reporting Adverse Events:

A serious adverse event can be classified as life threatening, requires inpatient hospitalization, persistent or significant disability or incapacity, or is an important medical event[51].

Participants will be monitored by a study therapist or study team member during all study visits. Study visits include baselines, follow up interviews, treatment groups, and focus groups. At the start of every session, the study team or therapist will hand out an independent sheet for each participant with the following questions,

1. “Have you had any significant/negative psychological, social, physical, or other negative life events in the last week? ”
2. How did this event make you feel?
3. When did this situation happen?

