4. Is the situation ongoing? If not what day/date did it end?
5. What this situation related to this treatment?

Once finished, the therapist will collect the document and check the response. The response to this question will be tracked and monitored each session. If the adverse events needs follow up, the therapist or study team member will have a conversation with the participant.

The study therapist and study team members will be required to notice any clinically significant changes in PTSD symptoms or any worsening symptoms and determine adverse events. The study team or study therapists will perform structured assessments (i.e., PCL-5, PHQ-9) each the beginning of each group. We will add a 15-minute period at the beginning of each group session specifically for check-ins and administration of the PCL-5 and PHQ-9. Scores from the PCL-5 and PHQ-9 will be reviewed during this period, and will be added to a tracking document that has separate columns for each measure at each timepoint assessment (i.e., baseline, group sessions, midpoint, post-treatment). The tracking document will also include columns to indicate whether the PCL-5 score has increased by 10 or more points and whether the participant reported a 1, 2, or 3 on item 9 of the PHQ-9. Additionally, a research staff member will stay in the treatment room to assist the study therapist with administration, review, tracking of the participant scores, and assessment of SI via the C-SSRS-SV as needed.

The study team will conduct the BDI-II at each timepoint assessment (baseline, mid-, post-, 1 month, 3 month follow up) . We will also use a tracking procedure to document BDI-II scores including whether the participant reported a 2 or 3 on item 9. Additionally, a research staff member will administer, review, and track the participant score, and assessment of SI via the C-SSRS-SV as needed.

Each change in the PCL-5 or the PHQ-9/BDI-II that meets the definition of an AE will be reported appropriately and tracked in REDCap.

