Guidelines for assessing the severity and study relatedness of each adverse events will follow the procedures outlined in Schnurr et al., 2022 and collaboratively determined by the study therapist and study team.

Severity:

Mild: Does not interfere with daily functioning/normal activities

Moderate: Interferes with normal activities to some extent

Severe: Interferes significantly with normal activities

Relatedness:

1. Not attributed to a study intervention
2. Possibly attributed to a study intervention
3. Attributed to a study intervention

An adverse event will be considered associated with the study if there is a reasonable possibility that the event was caused by the treatment or by an individual's participation in the research study. Any event with a reasonable causal relationship will be considered related.

The reporting period of adverse events begins from when participants sign the informed consent form until their final study visit (3-month follow-up visit), or until participants withdraw themselves from the study, whichever is sooner. All adverse events will be tracked using the Adverse Events tracking form. When adverse events occur, we will follow the Health Sciences IRB Unanticipated Problems Reporting Decision Tree.

Data and Safety Monitoring Plan/Data and Record Keeping:

We plan to utilize the UW ICTR Data Monitoring Committee (DMC) to oversee the study across all participating sites. The UW ICTR DMC is comprised of experienced members (core plus ad hoc) with expertise required to oversee this study. The DMC members will review protocol-specific reports created by statisticians using data pulled from the Research Electronic Data Capture (REDCap) data management tool. These standard reports will include an overview of study objectives, a review of actual and projected accrual rates, an evaluation of patient demographics for balance of randomization, and a summary of the number and seriousness of adverse events. An interim analysis of study results may be requested, and source documents may be reviewed to allow the DMC to independently judge whether the overall integrity and conduct of the protocol remain acceptable based on data provided and reported by the Principal Investigator. The DMC will make recommendations to the Principal Investigator that could include actions of continuation, modification, suspension, or termination.

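### The adverse-event sheet looks back only one week, so about two-thirds of the three months after session 12 is not covered by the general adverse-event question

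*Combined protocol and SAP*

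**What the plan says.** Monitoring and Reporting Adverse Events gives a five-question sheet: "At the start of every session, the study team or therapist will hand out an independent sheet for each participant". Question 1 reads "Have you had any significant/negative psychological, social, physical, or other negative life events in the last week". The later questions ask when the event happened and whether it is ongoing. The same section says "Study visits include baselines, follow up interviews, treatment groups, and focus groups", but does not state whether the sheet is also used at individual testing visits. No other question wording is given for follow-up.

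The section sets the collection window as follows: "The reporting period of adverse events begins from when participants sign the informed consent form until their final study visit (3-month follow-up visit"; withdrawal ends it sooner.

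The visit schedule is in Research Design and Procedures. For the 12 sessions, "These sessions will take place over 6 to 12 weeks, depending on session frequency". In the NIMH branch post-treatment testing is "within one week after completing treatment (group session 12"; in the WPP branch it is tied to week 6 of treatment. Follow-up testing is at one and three months. One follow-up CPT session is placed at 6 to 8 weeks in the WPP text, while the Treatment section describes it as typically 2 to 3 months after the course. NIMH participants also attend one focus group in the week after treatment.

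The PCL-5/PHQ-9 tracking document is to have "separate columns for each measure at each timepoint assessment (i.e., baseline, group sessions, midpoint, post-treatment". The Questionnaires section, however, schedules both measures at one and three months as well.

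**The concern.** The look-back period of question 1 matches the spacing of treatment sessions, not the spacing of follow-up visits. An event that starts and ends between two follow-up visits, outside the week before each, lies within the stated reporting period, yet the general question does not ask about it. The question on when an event happened does not help, because it dates only what question 1 has already elicited.

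The data monitoring committee reviews adverse events every six months. A low post-treatment count could be read as reassurance when it partly reflects not asking. Participants are incarcerated, and an event not elicited at the time may not be recoverable later.

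The tracking document has a smaller version of the same gap. It holds the flags for a 10-point PCL-5 increase and for PHQ-9 item 9, but lists no place for the 1-month and 3-month scores.

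**Working it through.** The documents give no coverage figure to reproduce. The check counts the days that lie within 7 days before at least one scheduled contact.

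**Inputs.** Look-back of 7 days (question 1). Session 12 is day 0. Post-test by day 7, one month taken as day 30, three months as day 91. Follow-up session at 6 to 8 weeks or 2 to 3 months. All visits are attended, and every study visit uses the sheet unless stated.

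**After session 12.** Days not asked about = 91 − days covered.

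| Timing assumed | Covered | Not covered | Share of 91 |
|---|---|---|---|
| Post-test day 7, 1 month, follow-up session at 6 weeks, 8 weeks or 2 months, 3 months | 4 × 7 = 28 | 63 | 69% |
| Post-test on day 3 instead | 3 + 3 × 7 = 24 | 67 | 74% |
| Follow-up session on the day of the 3-month visit | 3 × 7 = 21 | 70 | 77% |
| NIMH focus group adds a full separate week | 5 × 7 = 35 | 56 | 62% |
| Sheet used at group sessions only | 1 × 7 = 7 | 84 | 92% |

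If a WPP group runs for 12 weeks and post-test follows week 6, post-test falls before session 12. Three contacts then remain, again giving 91 − 21 = 70 days (77%).

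**Pre-treatment visit to 3-month visit.** Put the pre-treatment visit on day 0 and session 1 on day 14. Session windows cover day 7 to session 12 without a break.

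- 12-week course: session 12 on day 14 + 11 × 7 = 91; total 91 + 91 = 182 days; covered (91 − 7) + 28 = 112; not covered 70 (38%).
- 6-week course: session 12 on about day 14 + 38 = 52; total 52 + 91 = 143 days; covered (52 − 7) + 28 = 73; not covered 70 (49%).

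The 70 days are the 63 after session 12 plus 7 between the pre-treatment visit and session 1. Time from consent to the pre-treatment visit is not counted, because its length is not fixed.

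**Missed sessions.** On a weekly schedule each missed session leaves 7 further days unasked. The WPP stopping rules let a participant miss three sessions and stay in the group, which is up to 3 × 7 = 21 days.

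**With question 1 reworded.** If it asks about the time since the last contact, all 91 post-treatment days are covered at attended visits, against 28 now.

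**The case against.** Days covered are not the same as events captured. An event still present in the week before a visit can be reported however long ago it began. As an illustration, suppose every event lasts three weeks. Each visit then catches onsets over 7 + 21 = 28 days. With visits at days 7, 30, 49 and 91, only onsets between day 49 and day 91 − 28 = 63 are missed, which is 14 of 91 days. This stands. The 69% is a share of time, not of events lost.

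The sheet is also not the only safety measure. The PCL-5, BDI-II and PHQ-9 are given at one and three months. The C-SSRS-SV, when triggered, asks about ideation over the last month and about suicidal behavior. One-on-one talks about psychological, social, physical or medical problems have no one-week limit. This stands for much psychiatric deterioration, but the scales do not record physical, social or medical events. The weekly PHQ-9 has no stated end date, and the monitoring section ties it to group sessions. Department of Corrections records on clinical observation and restricted housing are optional and are not described as a source of adverse events.

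Overlapping windows in a twice-weekly group might suggest double counting. The start and stop dates already collected deal with that.

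A reader might also infer that the CPT arm is questioned far more often than the WPP controls, giving a spurious excess of events. The documents do not establish this. The enrollment text describes a waitlist and says "this group will receive the CPT treatment after the treatment group completes the treatment"; the WPP design text has controls completing a PCL-5 at each session; and the Treatment section has the control course matching CPT in frequency and duration. With parallel sessions there is no imbalance. With a waitlist, its size depends on when controls start their own sessions, which is not stated. No between-arm comparison of adverse events is specified either.

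**Conclusion.** The concern holds for the general adverse-event question after session 12: about 63 of 91 days (69%) fall outside its look-back, with a range of 62% to 92% across visit timings and readings of which visits use the sheet. These figures assume full attendance and the month lengths given above. The result does not depend on which timing of the follow-up session is meant.

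Two stronger readings should be avoided. A reader might infer that most of the whole reporting period goes unasked. That period starts at consent, and from the pre-treatment visit onward the uncovered share is about 38% to 49%. Nor are post-treatment events wholly unmonitored: the main loss is events that began and resolved between visits, especially physical, social or medical ones.

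This is a safety-reporting weakness that is worth correcting. No primary outcome is affected, and it does not call the design into question.

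**What to change.** - Reword question 1 to ask about the time *since your last study visit or session*, counting the consent visit as the first.
- State that the sheet is used at every study visit, including the individual testing visits at one and three months.
- Add 1-month and 3-month columns to the PCL-5/PHQ-9 tracking document.
- Reconcile the enrollment text, the WPP design text and the Treatment section on whether and when controls attend sessions, so that it is clear how often each arm is asked. Reconcile also the two timings of the follow-up CPT session.

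The cost is one reworded question, one clarifying sentence, two sets of columns and the reconciled text, with no new visits. The downside is longer recall: up to 91 − 30 = 61 days, about two months, at the 3-month visit if no follow-up session falls in between. That is preferable to not asking.
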